### 11.5 Analysis of Correlative Endpoints:

Because of the limited sample size inherent to phase II studies, the analysis of correlative endpoints is primarily exploratory. Standard descriptive methods will be used to summarize: 1) the role of CD30, CD68, and drug exporters on lymphoma specimens and 2) the role of T/B/NK cell subsets and BTK and ITK occupancy in the peripheral blood. If the combination is not found to have sufficient activity, these patterns may help explain the lack of activity. If sufficient activity is found, then participants who experience an objective response will be compared to those who did not in terms of correlates. Estimates of variation will also prove useful for future clinical research on this regimen. Formal testing of these comparisons is not planned. All analysis will clearly document the exploratory nature of these studies, although no attempt will be made to adjust for multiple comparisons inherent in correlative studies.

## **12.0 Data Handling, Data Management, Record Keeping**

### 12.1 Source Documents

Source documents are original documents, data, and records (e.g., medical records, pharmacy dispensing records, recorded data from automated instruments, laboratory data) that are relevant to the clinical trial. The Site Investigator or their designee will prepare and maintain adequate and accurate source documents. These documents are designed to record all observations and other pertinent data for each patient enrolled in this clinical trial. Source documents must be adequate to reconstruct all data transcribed onto the case report forms.

### 12.2 Data Capture Methods and Management

Data for this trial will be collected using Medidata RAVE, City of Hope's electronic capture system. Medidata RAVE is a web based, password protected system that is fully compliant with global regulatory requirements, including 21CRF Part 11 compliant.

Study personnel at each site will enter data from source documents corresponding to a subject's visit into the protocol-specific electronic Case Report Form (eCRF). A system of computerized data validation checks will be implemented and applied to the database on a regular basis. Queries are entered, tracked,

and resolved through the EDC system directly. The study database will be updated in accordance with the resolved queries. All changes to the study database will be documented.

The Data Coordinating Center will run monthly data expectation reports that will list any outstanding and overdue data. The Data Coordinating Center will send via email to the participating site a report monthly on any missing and/or overdue data forms. The participating site will be required to complete the missing and/or overdue data forms within 1 week of receipt of the report.

Query reports will be generated on a monthly basis by the Data Coordinating Center. The Data Coordinating Center will send via email to the participating site a report monthly on any outstanding queries.

The participating site staff (whether Principal Investigator or the staff collecting data at site) are required to take an eLearning Module within Medidata RAVE in order to obtain full access. The participating site staff will receive training via teleconference by COH DCC staff to review eCRFs that are specific to this protocol. Continuous training will be offered to participating sites if any amendments affect changes to the eCRFs during the course of the trial. The eCRFs within Medidata RAVE for this trial will have detailed instructions in the form of Help Text that provide instructions for completing each required field on each form.

### **12.3 Case Report Forms/Data Submission Schedule**

Study personnel at each site will enter data from source documents corresponding to a subject's visit into the protocol-specific electronic Case Report Form (eCRF) when the information corresponding to that visit is available.

The Investigator is responsible for all information collected on subjects enrolled in this study. All data collected during the course of this study must be reviewed and verified for completeness and accuracy by the Investigator. All case report forms must be completed by designated study personnel. The completed case report forms must be reviewed, signed and dated by the Site Investigator or designee in a timely fashion.

All data will be collected using electronic data collection system described in Section 12.2, and will be submitted according to the timelines indicated in Table 12.3.1.

All data will be collected within 1-2 weeks using standard Medidata Electronic Data Capture (EDC) case report forms. Data will be collected and stored on secure computers as indicated in 12.2. After 2 years, we will access the COH CIBMTR data repository to retrieve data regarding post-HCT long-term outcomes through study termination.

**Table 12.3.1 Data Submission Schedule**

Form	Submission Timeline
Eligibility Checklist	Complete prior to registration
On Study Forms	Within 10 business days of registration
Baseline Assessment Forms	Within 10 business days of registration
Treatment Forms	Within 10 business days of treatment administration
Adverse Event Report Forms	Within 5 business days For transplant patients: within 10 business days of the end of evaluation period.
Response Assessment Forms	Within 10 business days of response assessment

Other assessment forms (e.g. concomitant meds, transplant data including mobilization, etc.)	Within 10 business days of the assessment
Transplant Core Intake Form	Within 10 business days of stem cell infusion
Post Transplant Disease Assessment Form	Within 14 days of the end of evaluation period
Off Treatment/Off Study Forms	Within 10 business days of completing treatment or being taken off study for any reason
Follow up/Survival Forms	Within 10 business days of the protocol defined follow up visit date or call

## 12.4 Regulatory Records

The Investigator will maintain records, including updating records in accordance with Good Clinical Practice guidelines and FDA regulations. Additional information regarding required documents is provided in the DCC Operations Manual, a supplement to this protocol.

## 13.0 Adverse Events and Unanticipated Problems

---

### 13.1 Definitions

#### 13.1.1 Adverse Event (AE)

An adverse event is any untoward medical experience or change of an existing condition that occurs during or after treatment, whether or not it is considered to be related to the protocol intervention.

#### 13.1.2 Serious Adverse Event (SAE)

A serious adverse event is defined as *any expected or unexpected adverse events* that result in any of the following outcomes:

- Death
- Is life-threatening experience (places the subject at immediate risk of death from the event as it occurred)
- Unplanned hospitalization (equal to or greater than 24 hours) or prolongation of existing hospitalization
- A persistent or significant disability/incapacity
- A congenital anomaly/birth defect
- Secondary malignancy\*
- Any other adverse event that, based upon appropriate medical judgment, may jeopardize the subject's health and may require medical or surgical intervention to prevent one of the outcomes listed above (examples of such events include allergic bronchospasm requiring intensive treatment in the emergency room or at home, blood dyscrasias or convulsions that do not result in inpatient hospitalization, or the development of drug dependency or drug abuse).

\*Modified from the definition of unexpected adverse drug experience in <21 CFR 312.32>

#### 13.1.3 Unanticipated Problems Involving Risks to Subjects or Others

An unanticipated problem is any incident, experience, or outcome that meets all three of the following criteria:

1. Unexpected (in terms of nature, severity, or frequency) given the following: a) the research procedures described in the protocol-related documents such as the IRB approved research protocol, informed consent document or Investigator Brochure (IB); and b) the characteristics of the subject population being studied; **AND**
2. Related or possibly related to participation in the research (possibly related means there is a reasonable possibility that the incident, experience, or outcomes may have been caused by the drugs, devices or procedures involved in the research); **AND**
3. Suggests that the research places subjects or others at greater risk of harm (including physical, psychological, economic, or social harm) than previously known or recognized.

#### 13.1.4 Adverse Events of Special Interest (AESI)

Specific adverse events, or groups of adverse events, will be followed as part of standard safety monitoring activities. These events (regardless of seriousness) will be reported to Pharmacyclics Drug Safety per SAE reporting timelines.

##### 13.1.4.1 *Major Hemorrhage*

Major hemorrhage is defined as any of the following:

- Any treatment-emergent hemorrhagic adverse events of Grade 3 or higher\*. Any treatment-emergent serious adverse events of bleeding of any grade
- Any treatment-emergent central nervous system hemorrhage/hematoma of any grade

\*All hemorrhagic events requiring transfusion of red blood cells should be reported as grade 3 or higher AE per CTCAE v4.03.

Events meeting the definition of major hemorrhage will be captured as an event of special interest according to Section 13.1.4 above.

## 13.2 Assessment of Adverse Events

The site Investigator will be responsible for determining the event name, assessing the severity (i.e. grade), expectedness, and attribution of all adverse events.

#### 13.2.1 Assessment of Adverse Event Name and Grade

Adverse events will be characterized using the descriptions and grading scales found in the most recent version of CTCAE v4.03. A copy of the scale can be found at

<https://evs.nci.nih.gov/ftp1/CTCAE/About.html>. The determination of severity for all other events not listed in the CTCAE v4.03 should be made by the investigator based on medical judgment and the severity categories of Grade 1 to 5 as defined below:

- Grade 1 (mild) – An event that is usually transient and may require only minimal treatment or therapeutic intervention. The event does not generally interfere with usual activities of daily living.
- Grade 2 (moderate) – An event that is usually alleviated with additional specific therapeutic intervention. The event interferes with usual activities of daily living, causing discomfort but poses no significant or permanent risk of harm to the subject.
- Grade 3 (severe) – An event that requires intensive therapeutic intervention. The event interrupts usual activities of daily living, or significantly affects the clinical status of the subject.
- Grade 4 (life threatening) – An event, and/or its immediate sequelae, that is associated with an imminent risk of death or with physical or mental disabilities that affect or limit the ability of the subject to perform activities of daily living (eating, ambulation, toileting, etc).

- Grade 5 (fatal) – Death (loss of life) as a result of an event.

### 13.2.2 Assessment of Attribution

The following definitions will be used to determine the causality (attribution) of the event to the study agent or study procedure.

**Unrelated** -The event is clearly related to other factors such as the participant's clinical state, other therapeutic interventions, or concomitant medications administered to the participant.

**Unlikely** -The event is doubtfully related to the investigational agent. The event was most likely related to other factors such as the participant's clinical state, other therapeutic interventions, or concomitant drugs.

**Possible** –The event follows a reasonable temporal sequence from the time of drug administration, but could have been produced by other factors such as the participant's clinical state, other therapeutic interventions, or concomitant drugs.

**Probable** - The event follows a reasonable temporal sequence from the time of drug administration, and follows a known response pattern to the study drug. The event cannot be reasonably explained by other factors such as the participant's clinical state, therapeutic interventions, or concomitant drugs.

**Definite** - The event follows a reasonable temporal sequence from the time of drug administration, follows a known response pattern to the study drug, cannot be reasonably explained by other factors such as the participant's condition, therapeutic interventions, or concomitant drugs, AND occurs immediately following study drug administration, improves upon stopping the drug, or reappears on re-exposure.

### 13.2.3 Assessment of Expectedness

The following definitions will be used to determine the expectedness of the event:

- **Unexpected** - An adverse event is unexpected if it is not listed in the investigator's brochure and/or package insert; is not listed at the specificity or severity that has been observed; is not consistent with the risk information described in the protocol and/or consent; is not an expected natural progression of any underlying disease, disorder, condition, or predisposed risk factor of the research participant experiencing the adverse event. \*Modified from [21 CFR 312.32 \(a\)](#).
- **Expected** – An adverse event is expected if it does not meet the criteria for an unexpected event, OR is an expected natural progression of any underlying disease, disorder, condition, or predisposed risk factor of the research participant experiencing the adverse event.

## 13.3 Reporting of Adverse Events

### 13.3.1 Routine reporting of Non-Serious Adverse Events by Site Investigators

AEs will be collected from the signing of informed consent until ending study participation. Routine AE reporting will occur via data entry into the study eCRF. AEs will be monitored by the Protocol Management Team (PMT). Adverse events that do not meet the criteria of serious OR are not unanticipated problems do not require expedited reporting. AEs reported through expedited processes (i.e. reported to the IRB, DSMC, FDA, etc.) must also be reported in routine study data submissions.

AEs recorded in the eCRF include:

- Highest Grade for all toxicities
- All SAEs

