*Phase II experience:* 102 patients were treated in a multicenter pivotal phase II study of brentuximab vedotin. The dosing level and schedule was 102 patients relapsed post ASCT, using brentuximab vedotin 1.8 mg/kg intravenously every 3 weeks. The overall response rate was 75%, with 34% complete response rate and tolerable toxicity. The toxicity profile is similar to the phase I experience published by Younes et al. (2010). Treatment-emergent AEs (TEAEs) occurring in  $\geq 20\%$  of patients in the phase 2 studies were peripheral sensory neuropathy (44%), fatigue (42%), nausea (41%), diarrhea (34%), pyrexia (31%), upper respiratory tract infections (28%), neutropenia (21%), and vomiting (20%). These events were primarily mild to moderate and reversible. Approximately half of patients had treatment-emergent peripheral neuropathy, predominantly sensory neuropathy, with an onset and severity pattern consistent with a cumulative effect. Dose delay and subsequent reduction to 1.2 mg/kg was generally effective in managing peripheral neuropathy. Grade 3 and 4 neutropenia occurred in 13% and 7% of patients, respectively; these events were typically of short duration and well managed by brief dose delays with growth factor support in some cases. Infusion-related reactions occurred in approximately 10% of patients and were typically managed by dose interruption. Infusion-related reaction prophylaxis in subsequent treatment cycles was instituted at the discretion of the investigator. The clinical laboratory parameters for which the most patients had new or worsening shifts to  $\geq$ Grade 3 were low neutrophils (11%), lymphocytes (11%), platelets (6%), and leukocytes (5%); and high glucose levels (6%). Only 1 patient in the phase 2 studies had Grade 3 alanine aminotransferase (ALT) and Grade 3 aspartate aminotransferase (AST) levels. In the phase 2 studies, 31% of patients had an SAE, 28% had a Grade 3 or higher SAE, and 15% had an SAE that was determined by the investigator to be related to brentuximab vedotin. The most common SAE preferred terms (2%) were abdominal pain, disease progression (recurrent sALCL), pulmonary embolism, and septic shock. A higher proportion of patients with sALCL experienced SAEs, including deaths within 30 days of last dose, relative to patients with HL, likely due to the older age and the more aggressive nature of the malignancy in this patient population. Because of the high response rate and tolerability, BV was granted accelerated FDA approval for the treatment of relapsed/refractory HL following failed AHCT.

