### 13.3.2 Expediting Reporting Requirements of SAEs and UPs by Site Investigators

#### 13.3.2.1 *Criteria for Reporting SAEs/UPs to the Coordinating Center*

Serious Adverse Events meeting the criteria specified below will be reported to the Coordinating Center within **24 hours** of notification that the event occurred.

Adverse events that require expedited reporting include:

- AEs or SAEs that meet the definition of an unanticipated problem
- All deaths that occur within 30 days of active treatment
- All deaths that occur after 30 days of active treatment that are unexpected and possibly, probably, or definitely related to the study agent or procedure
- All serious adverse events, regardless of relationship to study agent or study procedure, that occur within 30 days of the last day of treatment
- All serious adverse events that occurred after 30 days of active treatment/therapy that are considered possibly, probably, or definitely related to the study agent or procedure

Note: Follow-up reports must be submitted for all events that require expedited reporting when the status of the event changes and until the resolution or stabilization of the event.

Reportable serious adverse events must be followed until the event is resolved, stabilized, or determined to be irreversible by the participating investigator; for ongoing reportable adverse events that are unrelated to study agent, the follow-up period may end at the 30-days post study-drug assessment. The Coordinating Center should be consulted prior to ending the follow-up of events that have stabilized.

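### Section 13.3.1 exempts from expedited reporting two classes of event that section 13.3.2.1 requires sites to expedite

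*Combined protocol and SAP*

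**What the plan says.** Section 13.3.1 is headed as covering routine reporting of non-serious events. Its exemption sentence reads: "Adverse events that do not meet the criteria of serious OR are not unanticipated problems do not require expedited reporting". The same section has sites record in the eCRF the highest grade of every toxicity and every SAE.

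Section 13.3.2.1 sets the expedited route and allows 24 hours from notification for SAEs that meet its criteria. Its list has these items:

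- Unanticipated problems, worded as "AEs or SAEs that meet the definition of an unanticipated problem".
- Two items on deaths: one for those close to active treatment, and one for later deaths that are both unexpected and at least possibly related.
- SAEs close to treatment, worded as "All serious adverse events, regardless of relationship to study agent or study procedure, that occur within 30 days of the last day of treatment".
- SAEs arising later, if their attribution is at least possible.

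Two definitions decide which events fall where. Section 13.1.2 defines an SAE to cover "any expected or unexpected adverse events" with a serious outcome. Section 13.1.3 is much narrower: "An unanticipated problem is any incident, experience, or outcome that meets all three of the following criteria". The three criteria are that the event is unexpected, at least possibly related to the research, and suggestive of more risk than was previously known.

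Table 12.3.1 makes adverse event forms due within 5 business days. For transplant patients they are due within 10 business days of the end of the evaluation period.

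**The concern.** The exemption joins two negated conditions with a capitalised OR, so failing either test takes an event off the expedited route. Only an event that is both serious and an unanticipated problem would stay on it. Section 13.3.2.1 asks for far more, and a site cannot follow both sections.

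What is at stake is the speed with which safety information reaches the coordinating center from four participating sites. The center depends on that flow for its own duties. Section 13.3.4.4, for example, gives the study PI 15 days from the event to send all SAEs, not only unanticipated problems, to the drug supplier. Time spent on the slower route comes out of those 15 days.

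**Working it through.** No sample size, power or error rate is involved, so the check compares the two rules class by class.

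**Inputs.** Let S mean serious (13.1.2) and U mean unanticipated problem (13.1.3).

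- 13.3.1, literal: exempt if (not S) OR (not U).
- 13.3.2.1: expedited if U; or if S and within 30 days of last treatment; or if S, later, and at least possibly related.

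**Comparison.**

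| Event | 13.3.1 as written | 13.3.2.1 | Result |
|---|---|---|---|
| S and U | not exempt | expedited | agree |
| S, not U, within 30 days | exempt | expedited | conflict |
| S, not U, later, at least possibly related | exempt | expedited | conflict |
| S, not U, later, unlikely related or unrelated | exempt | not listed | agree |
| U, not S | exempt | expedited | conflict |
| neither S nor U | exempt | not listed | agree |

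For events within 30 days of last treatment the table reduces to four classes (S yes/no by U yes/no), of which 2 of 4 conflict.

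**Are the conflicting classes real?** Yes. An SAE may be an expected event, whereas an unanticipated problem must be unexpected. Febrile neutropenia is an example. Section 6.1.2 lists it among the expected toxicities of brentuximab vedotin, and section 2.4.2 lists it among the frequent serious events with ibrutinib combinations. A hospitalisation for it would be an SAE but, unless its severity or frequency was out of line, not an unanticipated problem.

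**With AND.** The rule becomes: exempt if (not S) AND (not U). Only the last row is then exempt, and 0 of the 4 within-30-day classes conflict. For later SAEs not considered related, 13.3.1 no longer exempts them but 13.3.2.1 does not list them. That is why a sentence saying which section governs is needed as well as the changed word.

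**Length of the delay.** Table 12.3.1 does not say when the 5 business days start. If they start, like the 24 hours, when the site learns of the event, 5 business days normally span one weekend: 5 + 2 = 7 calendar days. Against 1 day, notification could be up to 7 − 1 = 6 calendar days later. For transplant patients it could be longer, but the table does not define the evaluation period, so no figure can be given.

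**The case against.** The best defence is that the documents show what was meant. The heading of 13.3.1 confines it to non-serious events. The section that follows is devoted to expedited reporting and is explicit about SAEs, and 13.3.3 sets out how SAEs and unanticipated problems are to be submitted. The sentence therefore looks like a slip for neither serious nor an unanticipated problem, and a careful site would probably follow 13.3.2.1.

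Much of this stands, and it limits the practical risk. It does not remove the contradiction. The sentence itself speaks of seriousness and of unanticipated problems, so it reaches beyond its heading. Even if the heading is taken at its word, a non-serious unanticipated problem falls squarely within 13.3.1 and is exempted there, while 13.3.2.1 lists it. Nothing in the protocol says which section prevails.

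A reader might also infer that dose-level or accrual-halt decisions would rest on incomplete counts. The documents do not support that. Unacceptable toxicity (5.1.7, 11.1.2, 11.3) is defined mainly by CTCAE grade, duration and attribution, not by seriousness or unanticipated-problem status. Lead-in decisions wait until three patients have been fully assessed after cycle 1, and the 33% rule is applied to each patient after cycle 1. Even a site following the literal wording of 13.3.1 still enters all SAEs in the eCRF.

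**Conclusion.** The sentence is wrong as written: it is an internal contradiction in an operative safety-reporting rule. It affects SAEs that are not unanticipated problems, if they occur within 30 days of last treatment or are later and at least possibly related, and it affects non-serious unanticipated problems. The consequence is later notification of the coordinating center, by days in the general case, and only at a site that applies 13.3.1 over 13.3.2.1. No endpoint, analysis, sample size or error rate is touched.

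Three further inferences should not be drawn.

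- *That most SAEs would be exempt.* The documents give no share of SAEs that are unanticipated problems. Section 2.4.1 reports that 31% of patients had an SAE and 15% one related to brentuximab vedotin. The ratio 15/31 = 48% counts patients rather than events and addresses only one of the three criteria, for one drug.
- *That about 12 of 39 patients would be affected (0.31 × 39 = 12.1).* The source states: "In the phase 2 studies, 31% of patients had an SAE, 28% had a Grade 3 or higher SAE". Those are single-agent studies that included systemic anaplastic large cell lymphoma, where the same section says SAEs were more frequent than in Hodgkin lymphoma. The product would estimate patients with any SAE, not delayed reports.
- *That 24 hours applies to non-serious unanticipated problems.* The sentence setting that limit names SAEs only. Such problems are on the expedited list, but no number of hours is literally stated for them.

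**What to change.** In 13.3.1, replace OR with AND, so that only events that are neither serious nor unanticipated problems are exempt. Add a sentence stating that the list in 13.3.2.1 governs which events are expedited. The cost is one word and one cross-reference; no treatment, assessment or analysis changes. While the text is open, the sponsor could also state the time limit intended for non-serious unanticipated problems, which 13.3.2.1 leaves implicit.
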